Sino-Nasal Outcome Test (SNOT-22) (If available): The questionnaire will be performed prior to any other study related procedures at Baseline and Weeks 8, 24, and at the early termination visit.

Pulmonary Exacerbation Evaluation: A modified version of the Fuchs criteria {Ramsey et al 2011, Wainwright et al 2015} will be used for categorization of pulmonary exacerbations at Baseline, Weeks 1, 2, 4, 6, 8, 9, 10, 12, 16, 20, 24, and at the early termination visit.

PK Blood Draws: Performed 2 hours after study drug administration at Baseline. Pharmacokinetic blood draws will be performed prior to study drug administration on Weeks 1, 2, 4, 6, 8, and at the early termination visit.

PK Sub-study: PPD

Anti-drug Antibodies (ADA): Baseline, Weeks 4, 8, 16, and 24, and at the 30-day Follow-Up Visit.

Safety Laboratory Tests: Complete blood count (CBC) with differential, chemistry panel will be collected at Screening, Baseline, Weeks 2, 4, 8, and 16, and at the Follow-up visit. Urinalysis will be collected at Screening, Baseline, Weeks 2, 8, and 16, and at the Follow-up visit.

Erythrocyte Sedimentation Rate (ESR): Collected at Screening, Week 8 and Week 24, and will be analyzed at the local lab.

Urine Cotinine: Screening and Weeks 4, 8, and 16.

Serum β -HCG (females of childbearing potential only): Screening and at the 30-Day Follow-Up Visit.

Urine Pregnancy Tests (females of childbearing potential only): Urine pregnancy tests will be performed at Baseline and at Weeks 2, 4, 6, 8, 9, 10, 12, 16, 20, and 24.

12-Lead ECG: Screening, Baseline, Week 4, 8, 16, 24, and the 30-day Follow-up visit.

Blood Biomarker Samples: Blood for biomarkers will be collected at Screening, Baseline, Weeks 2, 4, and 8, and at the 30-day Follow-up visit. Biomarker analysis will include but not limited to total and free MMP9, and MMP9 activity. A blood sample will be collected for RNA to study gene expression at Baseline, Weeks 4 and 8, Early Termination visit and at the 30-day Follow-up visit. Blood will also be collected from all subjects at Baseline for CF genotyping for subjects who do not have a historical genotyping available.

Optional Genomic Testing: PPD

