3.3. Study Treatments

3.3.1. Part 1

Subjects who meet the eligibility criteria at screening will be randomized in a blinded fashion in a 1:1 ratio as follows:

- Treatment arm (n=30): 600 mg GS-5745 (4 SC injections of 150 mg as 1 dose given weekly for 8 doses).
- Placebo arm (n=30): matching placebo (4 SC injections as 1 dose given weekly for 8 doses).

3.3.2. Part 2

Subjects who meet eligibility criteria at screening will be randomized in a blinded fashion in a 1:1:1 ratio as follows:

- Treatment arm 300 mg (n=30): 300 mg GS-5745 (2 SC injections of 150 mg as 1 dose given weekly for 8 doses).
- Treatment arm 150mg (n=30): 150 mg GS-5745 (1 SC injection of 150 mg and 1 SC injection of placebo as 1 dose given weekly for 8 doses).
- Placebo arm (n=30): matching placebo (2 SC injections as 1 dose given weekly for 8 doses).

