Screening Spirometry	X ^m																				

Week	Screening	Baseline Randomization	Optional PK	Study Drug Administration Visits						Optional PK	Study Drug Administration Visit	Primary Endpoint	Optional Open-Label Extension						30-Day Follow-Up Visit	Early Termination Visit	
				1	2	3	4	5	6				7	8	9	10	11, 13-15, 17-19, 21-23	12			16
Day	-30 to -1	1 ¹	5	8	15	22	29	36	43	48	50	57	64	71	85	113	141	169			
Window in days			±1	±3	±3	±3	±3	±3	±3	±1	±3	-3 to +4	±3	±3	±3	±3	±3	±3	±3	±7	
Home Health Visit Option						X		X		X	X				X						
Pre- and post-bronchodilator Spirometry ^e		X			X		X		X			X		X			X		X	X	X
PEFR	X	X ^p		X		X		X			X				X		X				
Chest X-ray ^f	X																				
ECG	X	X					X				X					X		X	X		
Induced sputum for biomarkers		X					X				X				X			X	X	X	
Spontaneous sputum for microbiology ^g	X, X				X				X								X				
FRI Scan ^h		X									X										
Blood for PK ⁱ		X		X	X		X		X		X									X	
PK sub-study			X						X												
Anti-drug Antibodies		X					X				X					X		X	X	X	
Blood for Biomarkers	X	X			X		X				X								X	X	
Blood for RNA Biomarkers		X					X				X								X	X	
Blood for CF genotyping ^l		X																			
Optional blood sample for genomic research ^l		X																			
Randomization		X																			
Study drug administration ^k		X		X	X	X	X	X	X		X	X ⁿ	X-weekly through week 23-X								
Adverse Events	X	X	X	X	X	X	X	X	X	X	X	X	X ^o	X ^o	X ^o	X ^o	X ^o	X	X	X	
Musculoskeletal Symptom Assessment	X	X					X				X				X	X	X	X	X		

a Questionnaires should be obtained prior to any other procedures. At visits where there are multiple questionnaires, the CFQR should be completed first, then SNOT-22 and then TSQM. If on a given visit SNOT-22 is not done then the CFQ-R is completed first and then the TSQM.

- b Includes height at screening visit and weight at all visits and to be conducted prior to dosing. A complete physical examination will be performed at screening and the 30-day Follow-up Visit. A symptom-driven physical examination will be performed at the Baseline, Week 4, 8, 12, 16, 20 and 24, and can be performed as needed at other study visits.
- c Safety labs include CBC with differential, chemistry panel.
- d For female subject post-menopausal for less than 2 years, if FSH < 40 mIU/ mL a serum pregnancy test will be required.
- e Subjects will withhold their standard of care inhaled CF therapies prior to study specific spirometry

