- n Study drug dosing will occur at Week 8 only for subjects who elect to enroll in the open-label extension and only after all other procedures have been completed.
- o Subjects enrolled into the open-label extension may request assistance administering the SC injections either by returning to the clinic or utilizing a home health care service provided by the Sponsor to ensure proper dosing and adherence. If determined acceptable by the DMC, home self-administration may be conducted in the OLE.
- p PEFR will be performed at Baseline only if baseline procedures are conducted over 2 days and induced sputum was conducted on Day -1 to confirm subjects are stable enough to be dosed.
- q As screening will occur over at least two different days, subjects should only be asked to withhold these medications the morning of their screening spirometry assessment and only after they have been properly consented.
- r To be conducted at the site's local lab.

Figure 6-1. Suggested Schedule for Key Screening and Baseline Procedures

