6.1.5. Week 8 (-3 to + 4): Primary Endpoint and Open-Label Extension

All Week 8 tests and procedures must be completed prior to participating in the OLE and dosing as indicated in [Table 6-1](#).

Subjects who agree to participate in the OLE portion of the study will be entered into the IXRS to confirm enrollment into the open-label extension after all other procedures as indicated in [Table 6-1](#). The first dose of open-label GS-5745 should be dispensed as directed by IXRS and administered to the subject at Week 8. Sites should train the subject on administration of the study drug at this visit. Subjects will be observed for 30 minutes after the last injection for the first 2 doses.

If the home health option is utilized during OLE, subjects will be dispensed GS-5745 at the visit prior to the scheduled home health visit for Weeks 11, 13 to 15, 17 to 19 and 21 to 23.

Subjects who do not agree to participate in the OLE portion of the study will be discontinued from the study and will be asked to return to the clinic in 30 days for their 30-day Follow-up visit as indicated in [Table 6-1](#).

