6.1.6. Utilization of Home Health Services

Weekly clinic visits during the study may pose a significant burden to study subjects. This burden must be balanced against the need to closely monitor these potentially vulnerable subjects during the early doses of study drug. Therefore, sites and subjects will have the option of utilizing a home health nursing organization provided by the Sponsor to complete visit procedures and study drug dosing during selected visits during the blinded and OLE portions of this study. Should the subject and site choose to utilize the home health service, blinded study visits at Weeks 3, 5, 7 and OLE visits at Weeks 11, 13 to 15, 17 to 19 and 21 to 23 may occur at the subject's home. The DMC and Gilead will be closely monitoring SC injection safety throughout the study. If it is judged in the OLE phase of the study that home self-administration without a home health provider present does not pose an unacceptable safety risk, then subjects may be trained for SC self-injection. Once the subject has successfully completed the self-administration training and is judged as capable of home SC self-administration of study drug by the trainer, the subject may begin self-administration of study drug at home without supervision at any of the remaining OLE visits mentioned above.

6.1.7. Open-Label Extension: Week 9 through 24

All OLE tests and procedures should be completed as indicated in [Table 6-1](#) for subjects participating in the OLE only.

At Week 9 and 10 site staff should instruct the subject on the packaging, storage, self-administration, and safe needle disposal for GS-5745. Following 2 successful doses in clinic within the OLE, subjects will be dispensed GS-5745 to administer Weeks 11, 13 to 15, 17 to 19, and 21 to 23 doses at home by a qualified home health service selected by the Sponsor to ensure proper dosing and adherence. In the OLE subjects will perform peak expiratory flow rate measurements prior to study drug administration on days when study spirometry is not performed. Doses should be administered at one week intervals (± 3 days), all injections for a single dose should be delivered within 1 hour, and the date/time of administration will be recorded. Please refer to the Pharmacy Manual for additional information.

6.1.8. 30-Day Follow-Up Visit

Thirty days after the last dose of study drug, subjects will return to the clinic for a follow-up visit. Procedures should be completed as indicated in [Table 6-1](#).

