#### 7.2.2.1. Treatment-Emergent Laboratory Abnormalities

Treatment-emergent laboratory abnormalities are defined as values within the reference range at baseline, but which become lower or higher than the reference range or values had a directional change in abnormality from baseline (eg, the value low at baseline became high at postbaseline visit) at any postbaseline time point, up to and including the date of last dose of study drug plus 30 days. If the relevant baseline laboratory value is missing, any postbaseline laboratory value that is lower or higher than the reference range will be considered treatment emergent.

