#### 7.2.2.2. Summaries of Laboratory Abnormalities

The summaries (number and percentage of subjects) for treatment-emergent laboratory abnormalities will be provided by lab test, treatment group and study phase; subjects will be categorized according to the most severe postbaseline abnormality grade for a given lab test.

For all summaries of laboratory abnormalities, the denominator is the number of subjects with nonmissing postbaseline values within study period.

A by-subject listing of treatment-emergent laboratory abnormalities will be provided by subject ID number and visit in chronological order. This listing will include all test results that were collected throughout the study for the lab test of interest, with all applicable severity grades displayed.

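### The SAP's 30-day limit on treatment-emergent laboratory abnormalities is shorter than the allowed follow-up visit window, so compliant late samples leave the numerator but can stay in the denominator

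*SAP*

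**What the plan says.** **Time limit.** SAP 7.2.2.1 accepts a post-baseline abnormality as treatment-emergent "up to and including the date of last dose of study drug plus 30 days". Protocol 8.6.3 uses a definition that runs to any time after Baseline, with no upper limit. SAP 7.7, the section for changes from the protocol's safety analyses, says only that summaries are limited because few subjects enrolled.

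**Laboratory schedule.** The protocol synopsis states: "chemistry panel will be collected at Screening, Baseline, Weeks 2, 4, 8, and 16, and at the Follow-up visit". Table 6-1 agrees and gives the follow-up visit a window of ±7 days.

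**Follow-up anchor.** Protocol 6.1.8 says: "Thirty days after the last dose of study drug, subjects will return to the clinic for a follow-up visit". Section 3.4 also counts from the last dose. Section 6.1.5, on the Week 8 visit, says that subjects who decline the OLE "will be asked to return to the clinic in 30 days for their 30-day Follow-up visit".

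**Last dose.** Section 3.3 gives eight weekly blinded doses. Table 6-1 footnote n adds: "Study drug dosing will occur at Week 8 only for subjects who elect to enroll in the open-label extension". For OLE subjects the dosing row of Table 6-1 reads "X-weekly through week 23-X".

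**What is tabulated.** SAP 7.2.1 drops descriptive statistics for laboratory tests, which leaves the treatment-emergent abnormality table as the only laboratory summary. For that table, SAP 7.2.2.2 states: "the denominator is the number of subjects with nonmissing postbaseline values within study period".

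**The concern.** A scheduled safety sample, drawn inside its permitted visit window, can be ruled out of the laboratory summary merely because the visit took place a day or more after the target. The denominator carries no matching limit, so the omission can only lower the reported percentage. For OLE completers the follow-up sample is the only safety lab after the last dose, and their previous one is at Week 16. The SAP also narrows the protocol's definition without declaring it. Separately, two protocol sections give different timings for the same visit in subjects who decline the OLE, so the length of post-dose observation depends on which one a site followed.

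**Working it through.** **Inputs.** Study day for Week w is 7w + 1, which matches Table 6-1 (Week 7 = Day 50, Week 8 = Day 57, Week 16 = Day 113). By the same rule Week 23 = Day 162. Window for Week 7: ±3 days; Week 8: −3 to +4; follow-up: ±7.

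**1. Last dose without OLE.** Eight weekly doses from Day 1: 1 + 7 × 7 = Day 50 (Week 7). The SAP cutoff is Day 50 + 30 = Day 80.

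**2. Follow-up counted from the last dose (protocol 3.4, 6.1.8).** The plan's figure of + 30 holds by definition. Allowed range: 30 ± 7 = +23 to +37, which is 15 days. Days past the cutoff: +31 to +37 = 7 of 15 (47%).

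**3. Follow-up counted from Week 8 (protocol 6.1.5).** Target: Day 57 + 30 = Day 87; 87 − 50 = last dose + 37. The + 30 of 6.1.8 is not reproduced. With Weeks 7 and 8 on their nominal days, the allowed range is Days 80 to 94, or +30 to +44. Only Day 80 meets the cutoff, so 14 of 15 days lie past it.

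**4. The same with the Week 7 and Week 8 windows.**
- Earliest target: (57 − 3) + 30 − (50 + 3) = +31.
- Latest target: (57 + 4) + 30 − (50 − 3) = +44.
- With ±7 added: +24 to +51.

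For a subject dosed at Week 7, the target under 6.1.5 is therefore always past the cutoff, although an early visit can still fall inside it.

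**5. OLE completers.** Last dose Day 162; follow-up target 162 + 30 = Day 192. Previous safety labs are on Day 113, which is 162 − 113 = 49 days before the last dose and 192 − 113 = 79 days before the follow-up target. If the follow-up visit is 1 to 7 days late, which is permitted, no lab after the last dose enters the numerator.

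**6. Numerator against denominator.** Take a subject whose values are normal until a first abnormal value on day +33. The subject has nonmissing post-baseline values and is counted in the denominator, but the abnormality is not counted. The documents do not give the split of the six subjects by arm. If an arm has 3 subjects, one omission moves its percentage by 1/3 = 33 points; with 2 to 4 subjects, by 50 to 25 points.

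**The case against.** The strongest defence is that 30 days is the plan's own convention. AEs are collected until 30 days after the last dose (protocol 7.3), and treatment-emergent AEs close at the same point (SAP 7.1.5.1). That makes the limit a legitimate choice, but it does not remove the mismatch: routine AE collection stops at that point, while scheduled labs may be drawn later, and neither SAP 7.7 nor the denominator reflects the limit.

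These points against a stronger reading stand:
- A reader might infer that follow-up labs are lost from the report. They are not. SAP 7.2 lists all hematology and chemistry results with abnormal values flagged, and the treatment-emergent listing in 7.2.2.2 shows every result for the test concerned.
- A reader might infer that all post-treatment labs are at risk. Subjects who decline the OLE also have Week 8 labs, nominally 57 − 50 = 7 days after the last dose. Subjects who withdraw have early-termination labs where possible.
- A reader might take 7 of 15 or 14 of 15 as a share of samples lost. These are counts of calendar days. The documents give no distribution of visit timing, and under 6.1.8 a visit on or before the target day still counts.
- Understatement is possible, not established. An abnormality counted earlier for the same test stays counted; only one first seen, or at its worst grade, after day +30 is affected.
- Protocol 6.1.5 is a single loosely worded sentence, whereas 3.4, 6.1.8 and the synopsis all count from the last dose.

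SAP 3.8.1 puts all data from Day 1 into the double-blind summaries for subjects who do not continue. That does not rescue a late value, because the more specific definition in 7.2.2.1 decides what counts as treatment-emergent.

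**Conclusion.** The point holds as a defect in a rule. The cutoff excludes some protocol-compliant follow-up samples from the numerator of the only laboratory summary, leaves the denominator unrestricted, and departs from protocol 8.6.3 without saying so. The exposure is days +31 to +37 under 6.1.8, and nearly the whole permitted range under 6.1.5. The 14-of-15 count assumes Weeks 7 and 8 on their nominal days and 6.1.5 read as 30 days from the Week 8 visit.

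The practical effect is small: six subjects, no inferential analysis, Part 2 not initiated, and flagged listings available. The documents do not show that any abnormality was actually missed. The group most exposed is OLE completers, because their follow-up sample is the only safety lab after the last dose.

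**What to change.** - In SAP 7.2.2.1, either replace the 30-day limit with the protocol's unrestricted period after Baseline, or extend it through the actual follow-up visit. A fixed limit of + 37 would not be enough: under 6.1.5 the permitted visit runs to +44 on nominal days and to +51 at the window extremes.
- If the limit is kept on purpose, record it in SAP 7.7 as a change from protocol 8.6.3, and apply the same limit to the denominator in 7.2.2.2.
- Protocol 6.1.5 must be reconciled with 3.4 and 6.1.8 on the follow-up anchor. As enrollment has ended, the CSR should state which was applied and give the actual days from last dose to the follow-up sample.

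The cost is one SAP clause and a sentence in the CSR. SAP Section 1 already provides for documenting changes made after SAP finalization in the CSR. The downside is that a few labs drawn more than 30 days after the last dose would count as treatment-emergent, and the laboratory window would differ from the 30-day AE window.

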#### 7.2.2.2. Summaries of Laboratory Abnormalities

The summaries (number and percentage of subjects) for treatment-emergent laboratory abnormalities will be provided by lab test, treatment group and study phase; subjects will be categorized according to the most severe postbaseline abnormality grade for a given lab test.

For all summaries of laboratory abnormalities, the denominator is the number of subjects with nonmissing postbaseline values within study period.

A by-subject listing of treatment-emergent laboratory abnormalities will be provided by subject ID number and visit in chronological order. This listing will include all test results that were collected throughout the study for the lab test of interest, with all applicable severity grades displayed.

#### 7.2.3. Liver-related Laboratory Evaluations

Liver-related laboratory evaluations will be presented as part of serum chemistry results.

#### 7.3. Body Weight and Vital Signs

Body weight and vital signs will not be summarized or listed.

#### 7.4. Prior and Concomitant Medications

Prior and concomitant medications will not be summarized or listed.

#### 7.5. Electrocardiogram Results

Electrocardiogram (ECG) data will not be summarized or listed.

#### 7.6. Other Safety Measures

A data listing will be provided for subjects experiencing pregnancy during the study.

#### 7.7. Changes From Protocol-Specified Safety Analyses

The limited efficacy and safety summaries are provided due to low number of subjects enrolled prior to the study termination.

## **9. SOFTWARE**

SAS® Software Version 9.4. SAS Institute Inc., Cary, NC, USA.

## 10. SAP REVISION

Revision Date (DD MMM YYYY)	Section	Summary of Revision	Reason for Revision

## 11. APPENDIX

### Appendix 1. Schedule of Assessments

	Screening	Baseline Randomization	Optional PK	Study Drug Administration Visits						Optional PK	Study Drug Administration Visit	Primary Endpoint	Optional Open-Label Extension						30-Day Follow-Up Visit	Early Termination Visit	
				1	2	3	4	5	6				7	8	9	10	11, 13-15, 17-19, 21-23	12			16
Week		Baseline		1	2	3	4	5	6	7	8	9	10	11, 13-15, 17-19, 21-23	12	16	20	24			
Day	-30 to -1	1l	5	8	15	22	29	36	43	48	50	57	64	71		85	113	141	169		
Window in days			±1	±3	±3	±3	±3	±3	±3	±1	±3	-3 to +4	±3	±3	±3	±3	±3	±3	±3	±7	
Home Health Visit Option						X		X		X	X			X							
Withhold all inhaled CF therapies morning of study visit	X q	X		X			X		X			X		X			X		X	X	
Written Informed Consent	X																				
CFQ-R a		X			X		X		X			X				X	X	X	X	X	X

	Screening	Baseline Randomization	Optional PK	Study Drug Administration Visits						Optional PK	Study Drug Administration Visit	Primary Endpoint	Optional Open-Label Extension						30-Day Follow-Up Visit	Early Termination Visit	
Week		Baseline	1	2	3	4	5	6	7	8	9	10	11, 13-15, 17-19, 21-23	12	16	20	24				
Day	-30 to -1	1 	5	8	15	22	29	36	43	48	50	57	64	71		85	113	141	169		
Window in days			±1	±3	±3	±3	±3	±3	±3	±1	±3	-3 to +4	±3	±3	±3	±3	±3	±3	±3	±7	
Home Health Visit Option						X		X		X	X				X						
TSQM (if available) a		X				X						X			X	X	X	X			
SNOT-22 (if available) a		X										X						X			
Medical History	X																				
Concomitant Medications	X	X	X	X	X	X	X	X	X	X		X	X	X		X	X	X	X	X	X
Pulmonary Exacerbation Evaluation		X		X	X		X		X			X	X	X		X	X	X	X	X	
Complete Physical Exam b	X																		X	X	

	Screening	Baseline Randomization	Optional PK	Study Drug Administration Visits						Optional PK	Study Drug Administration Visit	Primary Endpoint	Optional Open-Label Extension						30-Day Follow-Up Visit	Early Termination Visit	
Week		Baseline		1	2	3	4	5	6	7	8	9	10	11, 13-15, 17-19, 21-23	12	16	20	24			
Day	-30 to -1	1 l	5	8	15	22	29	36	43	48	50	57	64	71		85	113	141	169		
Window in days			±1	±3	±3	±3	±3	±3	±3	±1	±3	-3 to +4	±3	±3	±3	±3	±3	±3	±3	±7	
Home Health Visit Option						X		X		X	X			X							
Symptom Driven Physical Exam b		X					X					X			X	X	X	X			
Vital Signs	X	X		X	X	X	X	X	X		X	X	X	X	X	X	X	X	X	X	X
Blood for Safety Labs c	X	X			X		X					X				X			X	X	
ESR f	X											X							X		
Urine Cotinine	X						X					X				X					
Urinalysis	X	X			X							X				X			X	X	
Serum Pregnancy Test d	X																		X	X	

	Screening	Baseline Randomization	Optional PK	Study Drug Administration Visits						Optional PK	Study Drug Administration Visit	Primary Endpoint	Optional Open-Label Extension						30-Day Follow-Up Visit	Early Termination Visit	
Week		Baseline		1	2	3	4	5	6	7	8	9	10	11, 13-15, 17-19, 21-23	12	16	20	24			
Day	-30 to -1	1 l	5	8	15	22	29	36	43	48	50	57	64	71		85	113	141	169		
Window in days			±1	±3	±3	±3	±3	±3	±3	±1	±3	-3 to +4	±3	±3	±3	±3	±3	±3	±3	±7	
Home Health Visit Option						X		X		X	X				X						
Urine Pregnancy Test		X			X		X		X			X	X	X		X	X	X	X		
Oxygen Saturation		X										X								X	X
Screening Spirometry	X m																				
Pre- and post-bronchodilator Spirometry e		X			X		X		X			X		X			X		X	X	X
PEFR	X	X p		X		X		X			X		X		X		X				
Chest X-ray f	X																				
ECG	X	X					X					X				X		X	X		

	Screening	Baseline Randomization	Optional PK	Study Drug Administration Visits						Optional PK	Study Drug Administration Visit	Primary Endpoint	Optional Open-Label Extension						30-Day Follow-Up Visit	Early Termination Visit
Week		Baseline	1	2	3	4	5	6	7	8	9	10	11, 13-15, 17-19, 21-23	12	16	20	24			
Day	-30 to -1	1 l	5	8	15	22	29	36	43	48	50	57	64	71	85	113	141	169		
Window in days			±1	±3	±3	±3	±3	±3	±3	±1	±3	-3 to +4	±3	±3	±3	±3	±3	±3	±3	±7
Home Health Visit Option					X		X		X	X			X							
Induced sputum for biomarkers		X				X						X		X			X	X	X	
Spontaneous sputum for microbiology g	X, X				X			X								X				
FRI Scan h		X										X								
Blood for PK i		X		X	X	X		X				X								X
PK sub-study			X						X											
Anti-drug Antibodies		X				X						X			X		X	X	X	X
Blood for Biomarkers	X	X			X	X						X							X	X

	Screening	Baseline Randomization	Optional PK	Study Drug Administration Visits						Optional PK	Study Drug Administration Visit	Primary Endpoint	Optional Open-Label Extension						30-Day Follow-Up Visit	Early Termination Visit	
Week		Baseline		1	2	3	4	5	6	7	8	9	10	11, 13-15, 17-19, 21-23	12	16	20	24			
Day	-30 to -1	1 l	5	8	15	22	29	36	43	48	50	57	64	71		85	113	141	169		
Window in days			±1	±3	±3	±3	±3	±3	±3	±1	±3	-3 to +4	±3	±3	±3	±3	±3	±3	±3	±3	±7
Home Health Visit Option						X		X		X	X			X							
Blood for RNA Biomarkers		X					X					X								X	X
Blood for CF genotyping j		X																			
Optional blood sample for genomic research j		X																			
Randomization		X																			
Study drug administration k		X		X	X	X	X	X	X		X	X n	X-weekly through week 23-X								
Adverse Events	X	X	X	X	X	X	X	X	X	X	X	X	X	X o		X o	X o	X o	X	X	X

	Screening	Baseline Randomization	Optional PK	Study Drug Administration Visits						Optional PK	Study Drug Administration Visit	Primary Endpoint	Optional Open-Label Extension						30-Day Follow-Up Visit	Early Termination Visit	
Week		Baseline		1	2	3	4	5	6	7	8	9	10	11, 13-15, 17-19, 21-23	12	16	20	24			
Day	-30 to -1	1 l	5	8	15	22	29	36	43	48	50	57	64	71		85	113	141	169		
Window in days			±1	±3	±3	±3	±3	±3	±3	±1	±3	-3 to +4	±3	±3	±3	±3	±3	±3	±3	±7	
Home Health Visit Option						X		X		X	X				X						
Musculoskeletal Symptom Assessment	X	X					X					X				X	X	X	X	X	

- a Questionnaires should be obtained prior to any other procedures. At visits where there are multiple questionnaires, the CFQR should be completed first, then SNOT-22 and then TSQM. If on a given visit SNOT-22 is not done then the CFQ-R is completed first and then the TSQM.
- b Includes height at screening visit and weight at all visits and to be conducted prior to dosing. A complete physical examination will be performed at screening and the 30-day Follow-up Visit. A symptom-driven physical examination will be performed at the Baseline, Week 4, 8, 12, 16, 20, and 24, and can be performed as needed at other study visits.
- c Safety labs include CBC with differential, chemistry panel.
- d For female subject post-menopausal for less than 2 years, if FSH < 40 mIU/ mL a serum pregnancy test will be required.
- e Subjects will withhold their standard of care inhaled CF therapies prior to study specific spirometry
- f Chest x-ray will be obtained during the screening period if subject does not have a CT scan, MRI or chest x-ray obtained in the 90 days prior to Baseline.
- g Spontaneous and induced sputum should be obtained AFTER spirometry and FRI (if applicable) have been completed. If spontaneous sputum cannot be obtained, a throat swab may be used for microbiology culture. A second spontaneous sputum microbiology for culture will be collected in the screening period.
- h For subjects enrolled in the FRI sub-study only. Subjects will withhold their standard of care inhaled CF therapies prior to FRI.

- i At Baseline, PK should be obtained prior to and 2 hours after study drug administration. At all other visits with study drug dosing, PK should be performed prior to study drug administration. Subjects who consent to the optional PK sub-study will have one additional single PK sample collected at Day 5 ( $\pm 1$ ) and Day 48 ( $\pm 1$ ). Optional Day 5 PK and Day 8 should occur at least 1 day apart.
- j Blood for CF genotyping should be taken at baseline for subjects who do not have a historical genotype on file, but may be collected at any time during the study, if necessary. Blood for optional genomic research should only be taken from subjects who consented to this optional procedure. It should be taken at baseline, but may be collected at any time during the study, if necessary.
- k Observe subject for 2 hours after study drug administration on Day 1, and for 30 minutes after study drug administration at all other visits during the blinded phase of the study.
- l The baseline/randomization visit may be split over 2 days as needed. If the visit is split over 2 days, the following procedures should be done on the first day prior to standard of care inhaled CF therapies as indicated in protocol Section 5.5: questionnaires, urine pregnancy test (for women of childbearing potential only), oxygen saturation, pre- and post-bronchodilator spirometry, and FRI. Subjects must withhold their standard of care inhaled CF therapies again the next morning and perform spirometry prior to any remaining study procedures and study dosing. The day on which the first dose of study drug is administered is Baseline.
- m Two spirometry measures (pre-bronchodilator) taken at least 4 days apart (one during Screening, one at Baseline) must be taken to meet inclusion criterion 7.
- n Study drug dosing will occur at Week 8 only for subjects who elect to enroll in the open-label extension and only after all other procedures have been completed.
- o Subjects enrolled into the open-label extension may request assistance administering the SC injections either by returning to the clinic or utilizing a home health care service provided by the Sponsor to ensure proper dosing and adherence. If determined acceptable by the DMC, home self-administration may be conducted in the OLE.
- p PEFR will be performed at Baseline only if baseline procedures are conducted over 2 days and induced sputum was conducted on Day -1 to confirm subjects are stable enough to be dosed.
- q As screening will occur over at least two different days, subjects should only be asked to withhold these medications the morning of their screening spirometry assessment and only after they have been properly consented.
- r To be conducted at the site's local lab.
